10.6.2 KRYSTEXXA

Before administration of KRYSTEXXA, patients will be premedicated with antihistamines and steroids as described in [Section 10.5](#).

Patients will receive treatment with KRYSTEXXA on Day 0 and Day 14 of each Treatment Period for a total of 12 doses of study drug.

All study drugs should be administered through the same IV access. All blood samples should be drawn from an alternative venous access.

KRYSTEXXA will administered based on the manufacturer's currently approved labeling (*KRYSTEXXA Prescribing Information 2018*). Detailed instructions for study drug administration are provided in the Study Operations Manual.

Before administration, the diluted solution of KRYSTEXXA should be allowed to reach room temperature, but never exposed to artificial heating (eg, hot water, microwave). The diluted solution of KRYSTEXXA should be administered by IV infusion via gravity feed, syringe-type pump, or infusion pump over no less than 120 minutes. Following the infusion of KRYSTEXXA, the main IV line must be flushed with normal saline.

If an infusion reaction occurs, Investigators are permitted to use concomitant medications or treatments deemed necessary to provide adequate patient care. Investigators should also utilize the infusion reaction lab kit provided in the Study Operations Manual to collect additional blood specimens. In the case of a Grade 3 or 4 infusion reactions occurring during an infusion, the administration of study drug should be immediately discontinued, and the affected patient should be treated according to the clinical trial site's protocol for infusion reactions (e.g., monitoring, administration of antihistamines, corticosteroids, fluids and epinephrine, as clinically indicated).

10.7 Study Drug Accountability

Study drug will only be used as directed in the protocol. Study personnel will account for all vials of study drugs received, dispensed, and used for each patient, and vials returned. The date and time of reconstitution and dilution will be recorded. Used vials should be traceable back to the patient. The Investigator is responsible for the study drug accountability, reconciliation, and record maintenance. Refer to the Study Operations Manual for additional instructions.

10.8 Study Drug Handling and Disposal

Unused, partially used and empty vials will be stored until the Sponsor or Sponsor's representative instructs the site to return or dispose of the vials. Unused supplies will be returned or disposed of using appropriate documentation according to International Conference on Harmonization-Good Clinical Practice (ICH-GCP), local requirements, applicable Occupational Safety and Health Administration and Environmental Protection Agency regulations, and applicable study-specific procedures. Refer to the Study Operations Manual for additional instructions.

11. ASSESSMENT OF EFFICACY

11.1 Activity Assessment

11.1.1 Serum Uric Acid Assessment

The primary endpoint of this study is the comparison in the percentage of patients on SEL-212 vs. KRYSTEXXA who achieve and maintain reduction of SUA < 6 mg/dL for at least 80% of the time during Treatment Period 3 and Treatment Period 6.

Serum samples for measurement of SUA will be collected according to the schedules described in [Section 20](#). Methods used for processing samples and for measurement of SUA levels are described in the Study Operations Manual.

11.2 Gout Assessment

11.2.1 Gout Flare Assessment

Gout flare will be assessed as part of TEAE collection with severity determined as described in [Section 12.2.2.3](#).

11.2.2 Joint Assessment

Tender and/or swollen joints will be counted. The following joints will be assessed: metacarpophalangeal, proximal interphalangeal, and distal interphalangeal joints of the hands; the metatarsophalangeal and interphalangeal joints of the feet; shoulder, elbow, wrist, knee, ankle, tarsus, sternoclavicular, and acromioclavicular joints.

11.3 Health Questionnaires: Patient Reported Outcomes and Quality of Life Assessment

11.3.1 Health Assessment Questionnaire-Disability Index (HAQ-DI)

The HAQ-DI will be administered according to the schedules described in [Section 20](#).

The HAQ-DI, which includes the patient global assessment and pain scale, is an instrument that assesses fine movements of the upper extremity, locomotor activities of the lower extremity, and activities that involve both the upper and lower extremities. Standard scoring takes into account the use of aids and devices or assistance from another person. There are 20 items in 8 categories that represent a comprehensive set of functional activities: dressing, rising, eating, walking, hygiene, reach, grip, and usual activities. The stem of each item assesses a patient's functional ability using their usual equipment during the past week. Each category contains at least 2 specific sub-category questions. For example, under the category "walking," patients are asked about their ability to walk outdoors on flat ground and to climb up 5 steps.

11.3.2 Provider Global Assessment of Disease Activity

The Provider Global Assessment of Disease Activity (PrGA) will be conducted according to the schedules described in [Section 20](#). The PrGA will be administered to assess the severity of the

patient's disease on a scale from 0 (patient feels "very well") to 100 (patient feels "very poor"). Lower scores indicate less severe disease.

11.3.3 Short Form Health Survey 36 (SF-36)

The SF-36 will be administered according to the schedules described in [Section 20](#).

The SF-36 is a 36-item scale constructed to survey health status and quality of life ([Ware 1992](#)). The SF-36 assesses 8 health concepts: limitations in physical activities because of health problems; limitations in social activities because of physical or emotional problems; limitations in usual role activities because of physical health problems; bodily pain; general mental health (psychological distress and well-being); limitations in usual role activities because of emotional problems; vitality (energy and fatigue); and general health perceptions. The standard form of the instruments asks for patients to reply to questions according to how they have felt over the previous week.

12. ASSESSMENT OF SAFETY

12.1 Safety Parameters

12.1.1 Demographic/Medical History

Demographic and significant medical history will be documented according to the schedules described in [Section 20](#). Medical history will be recorded up to the time of dosing.

12.1.2 Concomitant Medications and Procedures

Concomitant medications and procedures will be documented according to the schedules described in [Section 20](#).

12.1.3 Vital Signs

Vital signs will be documented according to the schedules described in [Section 20](#).

Vital signs will include systolic blood pressure (mmHg), diastolic blood pressure (mmHg), pulse (beats per minute, bpm), respiratory rate (breaths per minute), and temperature (°C). Blood pressure and heart rate will be recorded after at least 5 minutes of rest in a sitting position.

12.1.4 Electrocardiogram (ECG)

A standard 12-lead ECG will be performed according to the schedules described in [Section 20](#).

12.1.5 Weight and Height

Weight (kg) and height (cm) will be performed according to the schedules described in [Section 20](#). Height will be measured at Screening only. Weight will be used to calculate study drug dosage as described in [Section 10.4](#).

12.1.6 Physical Examination

Physical examinations will be conducted according to the schedules described in [Section 20](#). Breast, rectal, and urogenital exams are not required unless warranted based on the clinical judgment of the patient's medical history or current medical condition. The physical exam should be done by a physician or physician's assistant or similarly qualified individual.

12.1.7 Tophus Assessment

Assessment of the presence of tophi will be conducted according to the schedules described in [Section 20](#). Patients will be stratified according to the presence of tophi (yes/no).

At the time of tophus assessment ([Section 20](#)), selected investigational sites will photograph tophi on the hands and feet in a subset of subjects for illustrative purposes. Detailed procedures for conducting the photography are provided in the Study Operations Manual.

12.1.8 Laboratory Assessments

All laboratory assessment will be conducted according to the schedules described in [Section 20](#). Procedures for processing samples are included in the study operations manual.

12.1.8.1 Hematology

Hematology assessments will include white blood cells (WBC) count with differential, red blood cell (RBC) count, hematocrit (Hct), hemoglobin (Hgb), mean corpuscular volume (MCV), mean corpuscular hemoglobin (MCH), mean corpuscular hemoglobin concentration (MCHC), red cell distribution width (RDW), platelet (Plt) count, mean platelet volume (MPV).

12.1.8.2 Blood Chemistry

Clinical chemistry assessments will include alkaline phosphatase, alanine aminotransferase (ALT), aspartate aminotransferase (AST), total bilirubin, blood urea nitrogen (BUN), creatinine, fibrinogen, glucose (fasting), phosphorous, and electrolytes (sodium, potassium, chloride, bi-carbonate, phosphate, and magnesium).

The following clinical laboratory assessments will be conducted only during Screening to determine eligibility for study participation: anti-PEG antibodies and G6PD.

12.1.8.3 Lipids

Lipid assessments will include total cholesterol, high-density lipoprotein (HDL), low-density lipoprotein (LDL), and triglycerides.

12.1.8.4 Coagulation

Coagulation assessments will include prothrombin time (PT), activated partial thromboplastin time (aPTT), international normalized ratio (INR).

12.1.8.5 Urinalysis

Urinalysis will include assessment of urinary protein, albumin, creatinine, pH, specific gravity, blood, glucose, ketones, bilirubin, leukocyte, esterase, WBC, RBC, crystals, casts (cast types), epithelial cells (renal and nonrenal), bacteria, mucus, and yeast.

At Screening only, urine will be collected for pregnancy testing ([Section 12.1.8.8](#)).

12.1.8.6 Anti-Drug-Antibodies

A blood sample for assessment of development of anti-drug-antibodies will be collected for possible future analysis.

12.1.8.7 Serology

Serology screening will include human immunodeficiency virus (HIV) antibodies 1 and 2, hepatitis-B surface antigen (HBsAg), and hepatitis-C antibody (HCVAb). If HCVAb is positive, then HCV virus level will be determined.

12.1.8.8 Pregnancy Screen

Samples for urine pregnancy testing (hCG) will be obtained.

Female partners of male patients who are of childbearing potential are required to practice an acceptable form of birth control to continue in the study and for 30 days after the last study drug administration. Male patients of reproductive potential who are having intercourse with female partners of childbearing potential must agree to use 2 forms of contraception, 1 of which must be a barrier method, during the study and for 90 days after the last study drug administration.

Acceptable barrier methods include a condom and diaphragm. Acceptable forms of birth control for female partners of childbearing potential are non-hormonal and hormonal intrauterine devices, hormonal birth control pills, hormonal birth control patches, hormonal birth control injections, hormonal birth control implants. Spermicide used alone is not an acceptable method and must be used with another acceptable form birth control method. Abstinence is acceptable if consistent with the patient's normal lifestyle.

If a patient becomes pregnant after she begins taking study drug, the procedures in [Section 12.2.2.7](#) should be followed.

12.1.8.9 Definition of Childbearing Potential and Acceptable Contraceptive Methods

A woman is considered of childbearing potential (i.e., fertile), following menarche and until becoming post-menopausal unless permanently sterile. Permanent sterilization methods include hysterectomy, bilateral salpingectomy, and bilateral oophorectomy.

A postmenopausal state is defined as no menses for > 24 months without an alternative medical cause. A high follicle stimulating hormone (FSH) level in the postmenopausal range may be used to confirm a post-menopausal state in women not using hormonal contraception or hormonal replacement therapy. However, in the absence of > 24 months of amenorrhea, one confirmatory FSH measurement must be obtained or documented.

For female partners of childbearing potential, the following methods of contraception, when used consistently and correctly, are considered reliable for participation in the study:

- Combined (estrogen and progestogen containing) hormonal contraception associated with inhibition of ovulation: oral, intravaginal, or transdermal
- Progestogen-only hormonal contraception associated with inhibition of ovulation: oral, injectable or implantable
- Intrauterine device (IUD)
- Intrauterine hormone-releasing system (IUS)
- Bilateral tubal; occlusion
- Vasectomized partner (provided that partner is the sole sexual partner and that vasectomized partner has received medical assessment of the surgical success)
- Sexual abstinence (refraining from heterosexual intercourse during the entire study period; the reliability of sexual abstinence needs to be evaluated in relation to the duration of the clinical study and the preferred and usual lifestyle of the patient)

12.1.9 Premedication Regimen

Refer to [Section 10.5](#) for procedures about premedication regimens to prevent infusion associated reactions and gout flare.

12.2 Adverse and Serious Adverse Events

12.2.1 Definition of Adverse Events

Definitions in this section are in accordance with 21 CFR 312.32.

12.2.1.1 Adverse Event (AE)

An AE is any untoward medical occurrence associated with the use of a drug (i.e., study drug) in humans, whether or not considered drug related. An AE can therefore be any unfavorable and unintended sign (including an abnormal laboratory finding), symptom, or disease temporally associated with the use of a drug and does not imply any judgment about causality. An AE can arise with use of any drug or medicinal product. A treatment-emergent AE (TEAE) is an AE that starts or worsens at any time after initiation of study drug on Day 0 of Treatment Period 1 until the End of Study Visit (30 days after completion of the last dose of study drug).

Patients will be considered enrolled in the study upon signing the ICF. During the Screening Phase (from time informed consent is signed to immediately before dosing) any clinically significant changes in the patient's health will be recorded in the patient's medical history and will not be considered as AEs. AEs will be collected from the time the patient is dosed (infusion is started) until the end of the End of Study Visit. SAEs will be collected from the time the patient signs informed consent until the End of Study Visit.

12.2.1.2 Serious Adverse Event (SAE)

An SAE is any AE that occurs irrespective of study treatment assignment, if it satisfies any of these criteria:

- Results in death;
- Is life-threatening;
- Requires inpatient hospitalization \geq 24 hours or prolongs existing hospitalization;
- Results in persistent or significant disability or incapacity or substantial disruption of the ability to conduct normal life functions;
- Is a congenital anomaly or birth defect;
- Is an important medical event that, based upon appropriate medical judgment, may jeopardize the patient or patient and may require medical or surgical intervention to prevent one of the outcomes listed above.

12.2.1.3 Suspected Adverse Reaction

A suspected adverse reaction is an AE for which there is a reasonable possibility that the drug caused the AE. For the purposes of IND safety reporting, "reasonable possibility" means there is evidence to suggest a causal relationship between the drug and the AE. Suspected adverse

reaction implies a lesser degree of certainty about causality than adverse reaction, which means any AE caused by a drug.

12.2.1.4 Unexpected Adverse Events and Unexpected Suspected Drug Reaction

An AE or suspected adverse reaction (an AE where there is a reasonable possibility that the drug caused the event; suspected drug related) is considered “unexpected” if it is not listed in the SEL-212 Investigator’s Brochure or is not listed at the specificity or severity that has been observed.

12.2.1.5 Infusion Reactions / Adverse Events of Special Interest

A study drug-related AE that occurs within 24 hours after initiation of study drug infusion will be assessed as an infusion reaction. An infusion reaction suspected to be anaphylaxis will be assessed according to the clinical criteria for the diagnosis of anaphylaxis based on the National Institute of Allergy and Infectious Diseases (NIAID) / Food Allergy & Anaphylaxis Network (FAAN) Symposium criteria ([Sampson 2006](#)).

Infusion reactions will be managed and treated as described below. In addition to premedication with antihistamines and steroids ([Section 10.5.2](#)), the following steps will be implemented in this protocol to either reduce the risk of infusion reactions or manage infusion reactions.

- Patients with immunoreactivity to PEG will be ineligible for the study
- Patients with prior exposure to uricase therapy will be ineligible
- Patients with a history of anaphylaxis or severe allergic reactions, angioedema, or previous infusion reactions will be excluded from the trial.
- Study drug will be administered at controlled rates only in a healthcare setting and by healthcare providers sufficiently equipped and prepared to manage infusion reactions including anaphylaxis.
- In case of infusion reaction, sites will perform specific assessments as specified in the Study Operations Manual.
- Each patient will be observed for infusion reactions after dosing of study drug in the clinic for approximately 1 hour after the end of study drug infusion. Patients will be informed about the signs or symptoms of infusion reactions and will be instructed to notify the Investigator immediately if they believe they are experiencing a reaction.
- Each patient shall remain for a minimum of 1 hour after the completion of infusion of study drug for a period of safety observation.
- Only sites with immediate capability to appropriately respond to a reaction of this severity will be allowed to participate in the trial to reduce the risk to any patient.

Adverse events of special interest (AESI) will be recorded specifically for occurrences of: gout flares, infections, viral infections, interstitial lung disease, stomatitis, infusion-related reactions including anaphylaxis, malignancies, renal failure; and the following lab tests, if deemed

clinically significant by the PI: hyperlipidemia, worsening of renal function tests, proteinuria, and leukopenia.

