7.7 Benefits and Risks

Chronic gout refractory to conventional therapy is a rare and serious condition associated with increased mortality rate and significantly decreased quality of life and for which there are very limited treatment options. Data from the Phase 2 study SEL-212/201 provide preliminary clinical evidence demonstrating that SEL-212 is a substantial improvement over available therapy:

- Substantially increased percentage of patients that maintain control of SUA while on therapy
- Substantially reduced gout flare rate during therapy
- Substantially reduced risk of infusion reactions
- More convenient to and greater compliance by patients because of once monthly therapy
- Acceptable safety at the doses to be studied in this Phase 2 study

SEL-212 has the potential to be an unprecedented safe and effective treatment option for patients for which other treatment options are inadequate. The overall balance between benefits and risks appears acceptable for the SEL-202/202 study of SEL-212 in the intended population of patients with chronic gout refractory to conventional therapy.

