10.6 Administration

10.6.1 SEL-212

Before administration of SEL-212, patients will be premedicated with antihistamines and steroids as described in [Section 10.5](#).

Patients will receive treatment with SEL-212 on Day 0 of each Treatment Period for a total of 6 doses of study drug.

All study drugs should be administered through the same IV access. All blood samples should be drawn from an alternative venous access.

If an infusion reaction occurs, Investigators are permitted to use concomitant medications or treatments deemed necessary to provide adequate patient care. Investigators should also utilize the infusion reaction lab kit provided in the Study Operations Manual to collect additional blood specimens. In the case of a Grade 3 or 4 infusion reactions occurring during an infusion, the administration of study drug should be immediately discontinued, and the affected patient should be treated according to the clinical trial site's protocol for infusion reactions (e.g., monitoring, administration of antihistamines, corticosteroids, fluids and epinephrine, as clinically indicated).

The reconstituted SEL-110.36 will be withdrawn from the vial and dosed via IV infusion with a syringe infusion pump utilizing an appropriately sized syringe. SEL-110.36 will be infused at a rate of 3.0 mL/hr for the first 30 minutes, then a rate adequate to deliver the remaining dose volume over a period of 60 minutes concurrently with 125 mL normal saline. Following the infusion of SEL-110.36, the main IV line must be flushed with normal saline prior to the start of the SEL-037 infusion. Refer to the Study Operations Manual for instructions regarding infusions for patients with medical history involving cardiovascular comorbidities.

SEL-037 infusion will start within 15 minutes after completion of the SEL-110.36 infusion. SEL-037 will be infused via infusion pump over a time period of no less than 120 minutes. If an infusion reaction occurs during the administration of SEL-037, the infusion may be slowed, or stopped and restarted at a slower rate at the discretion of the physician. Following the infusion of SEL-037, the main IV line must be flushed with normal saline.

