12.2.2 Recording Adverse Events

Patients will be encouraged to spontaneously report any changes in health from the time of signing the ICF through completion of the study. Study staff will also inquire about any changes in the patient's health.

All AEs will be recorded in the source document and the CRF. It is the responsibility of the Investigator to review all documentation (e.g., hospital progress notes, laboratory, and diagnostics reports) for the presence of AEs and for a complete evaluation of known AEs.

At minimum for each AE, the Investigator will evaluate and report the event name/term/description, onset (date and time), resolution (date and time), event severity/intensity, relationship to study drug, action taken in regard to study drug, whether the event is an SAE, and whether or not it caused the patient to discontinue the study. The event time is only required while the patient is in the clinic.

During the Screening Phase (from time informed consent is signed to immediately before dosing) any clinically significant changes in the patient's health will be recorded in the patient's medical history and will not be considered as AEs.

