12.2.2.2 Relationship to Study Drug

The Investigator is obligated to assess the relationship between study drug and the occurrence of each AE. The Investigator will use clinical judgment to determine the relationship. Alternative causes, such as natural history of the underlying diseases, concomitant therapy, other risk factors, and the temporal relationship of the event to the study drug will be considered and investigated. The Investigator will also consult the SEL-212 Investigator's Brochure and/or Product Information for marketed products in the determination of his/her assessment.

The Investigator will assess causality as to whether the event is related or not related to study drug based on the following definitions:

- Not Related: If no valid reason exists for suggesting a relationship to study drug or the AE was more likely explained by causes other than study drug.
- Unlikely to be Related: Onset of the event has a reasonable temporal relationship to study drug administration and although a causal relationship is unlikely, it is biologically plausible.

- Possibly Related: Onset of the event has a strong temporal relationship to administration of the study drug and a causal relationship is biologically plausible
- Related: The study drug dosing and AE were closely related in time and the AE may be explained by exposure to study product: e.g., known pharmacological effect or recurrence on re-challenge.

There may be situations, particularly when an SAE has occurred, where the Investigator has minimal information to make an assessment in an initial SAE report. However, it is very important that the Investigator always makes an assessment of causality for every SAE prior to transmission of the SAE report. The Investigator may change his/her opinion of causality in light of follow-up information, amending the SAE report accordingly. Any assessment of causality made by the Investigator should also be documented in the patient's source medical record.

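### Infusion reactions are defined by a 24-hour clock, but onset time is required only in the clinic, so events dated the day after an infusion cannot be reliably classified.

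*Protocol*

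**What the plan says.** Protocol Section 12.2.1.5 sets two conditions for an infusion reaction, relatedness and timing: "A study drug-related AE that occurs within 24 hours after initiation of study drug infusion will be assessed as an infusion reaction". Infusion-related reactions, including anaphylaxis, are adverse events of special interest in the same section. The required stay is also given there: "Each patient shall remain for a minimum of 1 hour after the completion of infusion of study drug for a period of safety observation".

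Section 12.2.2 lists onset date and time among the minimum data for each adverse event, then limits the time: "The event time is only required while the patient is in the clinic". The date is not limited in this way.

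Under Section 12.2.2.2 the investigator judges relatedness, consulting the SEL-212 Investigator's Brochure and/or "Product Information for marketed products in the determination of his/her assessment". Section 7.6.1 makes treatment open-label and confines assessor blinding to the health questionnaires and joint assessment.

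SAP Section 5.9 does not impute missing data unless specified, and nothing is specified for adverse event times. SAP Section 8.3 summarises adverse events of special interest, which the medical monitor is to define before database lock. It has no rule for placing an event without a time inside or outside the 24 hours.

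**The concern.** A rule counted in hours needs an hour of onset. The plan asks for one only for the first few hours of the window, and the patient spends the rest of it elsewhere. No early visit fills the gap. In Treatment Periods 1, 2, 4 and 5 the next scheduled visit after an infusion is Day 21 for SEL-212 (Appendix A) and about 14 days later for Krystexxa (Appendix C). An onset time not volunteered promptly would have to be recalled much later.

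Infusion reactions are a main named risk of uricase therapy. Protocol Section 5.5 reports them in about 26% of Krystexxa patients, and Section 7.7 lists among the advantages of SEL-212 seen in Phase 2: "Substantially reduced risk of infusion reactions". Readers will compare the two arms on this event, so the count should follow from a rule that the collected data can support. The other half of the definition, relatedness, rests on an unblinded judgement. The table of related events therefore cannot show by itself how far it depends on that judgement.

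**Working it through.** **Step 1. Time in the clinic from the start of infusion, at the minimum stay.**

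- SEL-212 (Protocol Section 10.6.1). The first component takes 0.5 h ("SEL-110.36 will be infused at a rate of 3.0 mL/hr for the first 30 minutes") plus 1.0 h ("over a period of 60 minutes concurrently with 125 mL normal saline"). The second takes at least 2.0 h, and observation 1.0 h. Sum: 0.5 + 1.0 + 2.0 + 1.0 = 4.5 h, matching the last Day 0 sampling time in Appendix B. With the permitted 15-minute gap between components it is 4.75 h.
- Krystexxa (Section 10.6.2). Infusion takes at least 2.0 h and observation 1.0 h. Sum: 3.0 h, matching Appendix D.

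**Step 2. Window hours with no required clock time.**

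- SEL-212: 24 − 4.5 = 19.5 h, or 19.5/24 = 81%.
- Krystexxa: 24 − 3.0 = 21 h, or 21/24 = 88%.

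These hours lack a required time, but many of them can still be classified from the date.

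**Step 3. What the date settles.** Let the infusion start at clock hour s, with discharge the same day. The window runs to hour s of the next day.

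- After discharge, same date: 24 − s − stay. An event known to have started after discharge and dated that day is inside the window.
- Next calendar date: this day covers 24 − s to 48 − s hours after the start. The part inside the window is 24 − (24 − s) = s hours; the other 24 − s hours are outside. The date alone cannot separate them.

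The documents give no start times, so the values of s below are assumptions. The clock is taken from the start of the first component.

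| Assumed start | Arm | In clinic (h) | After discharge, same date (h) | Next date, inside window (h) |
|---|---|---|---|---|
| 08:00 | SEL-212 | 4.5 | 11.5 | 8 |
| 08:00 | Krystexxa | 3.0 | 13.0 | 8 |
| 09:00 | SEL-212 | 4.5 | 10.5 | 9 |
| 09:00 | Krystexxa | 3.0 | 12.0 | 9 |
| 14:00 | SEL-212 | 4.5 | 5.5 | 14 |
| 14:00 | Krystexxa | 3.0 | 7.0 | 14 |

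Each row sums to 24. With a 09:00 start, an event dated the next day began 15 to 39 h after the start, and only the first 9 of those 24 hours count. At equal start times the unresolved part is the same in both arms, because it depends on s and not on the length of stay.

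**Step 4. Number of windows.** Protocol Section 7.1.2 allows up to 6 SEL-212 and up to 12 Krystexxa infusions. A full course opens 6 × 24 = 144 and 12 × 24 = 288 window hours. Per patient, the chances for an event to fall in a window are therefore up to 2 to 1, although each window has the same unresolved part.

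**The case against.** **The gap is narrower than it first appears.** A reader might infer from Step 2 that 81% and 88% of the window is unclassifiable and that the shortfall differs by arm. The documents do not support that. The onset date is always required and settles events after discharge on the infusion day. What remains is the next calendar day, plus the occasional same-day event that may have begun at home before the infusion. Stay lengths are also minimums, so a slower infusion shortens the untimed stretch. This objection stands and sets the size of the point.

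**Times may be recorded anyway.** Section 12.2.1.5 tells patients to notify the investigator immediately of a suspected reaction and refers sites to the Study Operations Manual for specific assessments. Nothing forbids recording a time at home. The manual and eCRF are not among the documents and might collect it. This is fair, but the protocol's own rule does not require the time.

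**Relatedness need not be biased.** A reader might also infer that investigators would label the same event a reaction on Krystexxa and unrelated on SEL-212. The documents do not support a direction. Investigators may consult sources for either product, Section 7.6.1 says that the two proteins carry similar risks, and anaphylaxis is judged by external criteria. Open-label judgement remains a risk of unknown direction.

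**The consequences are limited.** Infusion-reaction incidence is not a confirmatory test. The Kaplan-Meier and log-rank analysis in SAP Section 6.1 that includes infusion-related reactions concerns treatment discontinuation by reason, not the 24-hour clock. SAP Section 8.3 already tabulates all treatment-emergent events whatever their causality, though not restricted to 24 hours after an infusion.

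**Conclusion.** The point holds for events dated the calendar day after an infusion. Under the recording rule as written, such an event has a date but no required time, and the definition cannot reliably place it inside or outside the window. With assumed starts between 08:00 and 14:00, the affected part is 8 to 14 of the 24 hours per infusion, equal in the two arms at equal start times. It would be larger for later starts.

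These are shares of window time, not of reactions. The documents do not say how many reactions begin the next day or in which direction misclassification would move the comparison. The conclusion that delayed reactions in general cannot be classified goes too far, since same-day events after discharge can be. A claim of bias for or against either product would also go beyond the documents.

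**What to change.** **Required change.** Amend Protocol Section 12.2.2 and the eCRF completion rule so that onset date and time are required, patient-reported if at home, for every adverse event starting on an infusion day or the next calendar day. This covers the whole 24-hour window for any start time and also separates same-day events that preceded the infusion. The cost is a small recording burden for sites and patients.

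**Optional addition.** Because relatedness is judged open-label, add to SAP Section 8.3 a supportive table of treatment-emergent events with onset within 24 hours of the start of an infusion, regardless of causality. Show it beside the protocol-defined table of related events. Report it per infusion as well as per patient, because with up to 12 infusions against 6 a per-patient count alone would collect coincidental events at up to about twice the rate in the Krystexxa arm. The cost is one extra table that will contain some coincidental events.
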